4.3. Protocol Deviations

A summary of important protocol deviations will be provided by the Clinical Operations group for subjects in the Safety Analysis Set.

5. BASELINE CHARACTERISTICS

5.1. Demographics

Subject demographic variables (ie, age, sex, race, and ethnicity) will be summarized. Age will be summarized using descriptive statistics (n, mean, SD, median, Q1, Q3, minimum, and maximum). Age categories (< 65 years, \geq 65 years), sex, race, and ethnicity will be summarized as the number and percentage of subjects. Age is calculated in years on the date of first dose of study drug. For this study, only the year of the birthdate will be reported in eCRFs per country regulations; the month and day will be set to January 01 for purposes of calculating the subject's age. If a subject did not receive study drug after enrollment, the subject's age will be calculated from the date that the subject signed the informed consent form. The summary of demographic data will be provided for the "SOF/VEL 12 Weeks" group for the Safety Analysis Set, and by HCV Genotype and Overall for the FAS (as described in Section 3.2 of this SAP).

A by-subject demographic listing will be provided by subject ID number in ascending order.

5.2. Other Baseline Characteristics

Other baseline characteristics include:

- HCV genotype (for this study a separate table will be produced by HCV genotype and by subtype within each genotype)
- baseline body mass index (BMI; in kg/m^2) as a continuous variable and as categories ($< 30 \text{ kg}/\text{m}^2$, $\geq 30 \text{ kg}/\text{m}^2$)
- IL28B (CC, non-CC; with non-CC further broken down to CT, TT)
- baseline HCV RNA (\log_{10} IU/mL) as a continuous variable and as categories ($< 800,000 \text{ IU/mL}$, $\geq 800,000 \text{ IU/mL}$)
- baseline ALT (U/L) as a continuous variable and as categories ($\leq 1.5 \times \text{ULN}$, $> 1.5 \times \text{ULN}$)
- cirrhosis (no, yes)
- baseline estimated creatinine clearance (eCrCl) using the Cockcroft-Gault equation
- prior HCV treatment (treatment-naive, treatment-experienced)
- most recent HCV treatment (DAA \pm PEG + RBV, IFN \pm RBV, PEG \pm RBV) for treatment-experienced subjects
- most recent HCV treatment response (non-responder, relapse/breakthrough, early treatment discontinuation, unknown) for treatment-experienced subjects

- years from most recent liver transplantation on date of first dose of study drug
- prior HCV treatment experience and cirrhosis status (treatment naive with cirrhosis, treatment-experienced with cirrhosis, treatment naive without cirrhosis, treatment-experienced without cirrhosis)

Estimated creatinine clearance will be calculated by the Cockcroft-Gault method: $eCrCL_{CG}$ (mL/min) = $[(140 - \text{age (yrs)}) \times \text{weight (kg)} \times (0.85 \text{ if female})] / (\text{serum creatinine (mg/dL)} \times 72)$, where weight is actual weight in kilograms.

The summary of demographics and baseline characteristics will be provided for the “SOF/VEL 12 Weeks” group for the Safety Analysis Set; and overall and by HCV Genotype for the FAS (using the groupings described in Section 3.2 of this SAP). Continuous variables will be summarized using descriptive statistics (n, mean, SD, median, Q1, Q3, minimum, and maximum) and categorical variables using the number and percentage of subjects.

A summary of immunosuppressants administered at baseline to prevent rejection of the liver transplant will be presented for the Safety Analysis Set.

A by-subject listing of baseline characteristics will be provided by subject ID number in ascending order. The type of assay used to determine the HCV genotype (Abbott RealTime HCV genotype II assay [ie, LiPA 2.0] or Sanger NS5B population genotype and subtype and the corresponding results will also be displayed in this listing).

A separate by-subject data listing for cirrhosis determination will be provided for all subjects at screening.

A separate by-subject data listing of liver imaging results performed within 6 months of Day 1 to screen for hepatocellular carcinoma for subjects with cirrhosis will be provided.

A separate by-subject data listing for prior HCV treatment and response will be provided for all subjects who took prior HCV medications. The listing will display the prior HCV regimen and treatment, the treatment duration, and the prior HCV treatment response for treatment-experienced subjects.

5.3. Medical History

A by-subject listing of disease-specific medical history will be provided by subject ID number (in ascending order).

6. EFFICACY ANALYSES

6.1. Primary Efficacy Endpoint

6.1.1. Definition of the Primary Efficacy Endpoint

The primary efficacy endpoint is SVR12 defined as HCV RNA < LLOQ (ie, < 15 IU/mL) 12 weeks after discontinuation of the study drug in the FAS. The COBAS® AmpliPrep/COBAS® TaqMan® HCV Quantitative Test, v2.0 will be used to measure HCV RNA.

6.1.2. Statistical Hypothesis for the Primary Efficacy Endpoint

No hypothesis testing will be performed.

6.1.3. Primary Analysis of the Primary Efficacy Endpoint

The estimate of SVR12 and a 2-sided 95% exact CI based on the Clopper-Pearson method will be provided for the “SOF/VEL 12 Weeks” group {[Clopper 1934](#)}. In addition, point estimates and 95% confidence intervals will be provided by HCV genotype (as described in Section [3.2](#) of this SAP).

6.1.4. Subgroup Analysis of the Primary Efficacy Endpoint

Point estimates and the 2-sided 95% exact CI based on the Clopper-Pearson method will be provided for the SVR12 rate overall and by HCV genotype (1 total [and further broken down for 1a and 1b], 2, 3, 4, 5, and 6) for each subgroup outlined in Section [3.4](#). SVR12 rates will be summarized by categories of early viral response to explore possible early on-treatment predictors of SVR12.

6.2. Secondary Efficacy Endpoints

6.2.1. Definition of Secondary Efficacy Endpoints

Secondary efficacy endpoints include the following:

- The proportion of subjects with HCV RNA < LLOQ at 4 weeks after discontinuation of study treatment (SVR4)
- The proportion of subjects with HCV RNA < LLOQ while on treatment by study visit
- HCV RNA (\log_{10} IU/mL) and change from baseline in HCV RNA (\log_{10} IU/mL) by visit through end of treatment (EOT)

- The proportion of subjects with virologic failure as the following
 - On-treatment virologic failure
 - HCV RNA \geq LLOQ after having previously had 2 consecutive HCV RNA $<$ LLOQ, while on treatment, confirmed with 2 consecutive values (note, second confirmation value can be posttreatment), or last available on-treatment measurement with no subsequent follow up values (ie, breakthrough)
 - $> 1 \log_{10}$ IU/mL increase in HCV RNA from nadir while on treatment, confirmed with 2 consecutive values (note, second confirmation value can be posttreatment), or last available on-treatment measurement with no subsequent follow up values (ie, rebound)
 - HCV RNA persistently \geq LLOQ through 12 weeks of treatment (ie, nonresponse)
 - Relapse
 - HCV RNA \geq LLOQ during the posttreatment period having achieved HCV RNA $<$ LLOQ at EOT, confirmed with 2 consecutive values or last available posttreatment measurement
- Characterization of HCV drug resistance substitutions at baseline, during, and after therapy with SOF/VEL

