##### **Efficacy Results**

The study met the primary efficacy endpoint. The SVR12 rate for the SOF/VEL 12 Week group was statistically noninferior to the SVR12 rate for the SOF+RBV 24 Week group. The SVR12 rates were as follows:

- SOF/VEL 12 Week group: 95.3% (95% CI: 92.1% to 97.5%) of subjects (264 of 277) achieved SVR12.
- SOF+RBV 24 Week group: 80.4% (95% CI: 75.2% to 84.9%) of subjects (221 of 275) achieved SVR12.

The strata-adjusted difference (95% CI) in the proportions was 14.8% (9.6% to 20.0%). The superiority of treatment with SOF/VEL for 12 weeks over SOF+RBV for 24 weeks for SVR12 was also demonstrated ( $p < 0.001$ ; CMH test stratified by cirrhosis status and prior treatment experience).

In the SOF/VEL 12 Week group, 13 of 277 subjects (4.7%) did not achieve SVR12. Of these, no subjects had on-treatment virologic failure, 11 subjects relapsed, and 2 subjects were lost to follow-up. In the SOF+RBV 24 Week group, 54 of 275 subjects (19.6%) did not achieve SVR12. Of these, 1 subject had on-treatment virologic failure (nonresponse), 38 subjects relapsed, and 15 subjects did not achieve SVR12 for reasons other than virologic failure. These 15 subjects included 6 subjects who were lost to follow-up or who did not attend a post-treatment Week 12 visit, 4 subjects who withdrew from the study due to AEs, 2 subjects who withdrew consent from the study, 2 subjects who died, and 1 subject who only received 2 days of study drug, did not achieve HCV RNA  $<$  LLOQ on treatment, and did not meet the protocol definition for virologic failure.

Most relapses occurred by the post-treatment Week 4 visit. In the SOF/VEL 12 Week group, 8 of 11 relapses occurred by post-treatment Week 4, and 3 of 11 relapses occurred between post-treatment Weeks 4 and 12.

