### **Virologic Resistance**

Pretreatment NS5A and NS5B NI RAVs were present in 16% and 4% of subjects, respectively, in the SOF/VEL 12 Week group. There was a numerically lower SVR12 rate in SOF/VEL-treated subjects with baseline NS5A RAVs compared with subjects without NS5A RAVs (88% vs 97%, respectively). All subjects with NS5B NI RAVs in the SOF/VEL 12 Week group achieved SVR12.

A total of 10 subjects in the SOF/VEL 12 Week group relapsed, and 1 subject was reinfected. All 10 subjects had the NS5A RAV Y93H detected at relapse time points. No SOF/VEL-treated subjects had NS5B NI RAVs emerge at relapse. The NS5B NI RAVs (N142T, L159F, or V321A) emerged in 7 of 39 subjects in the SOF+RBV 24 Week group who had virologic failure.

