#### **6.6.8. HCV Viral RNA Sequencing/ Phenotyping (Archive)**

Plasma samples will be collected at Baseline/Day 1 and each subsequent visit for HCV viral sequence analysis. At any unscheduled visit initiated for the purpose of confirming HCV virologic breakthrough, HCV viral sequence/phenotype plasma sample must also be collected. Unused samples may be archived.

Details regarding the collection, processing, and shipping of samples will be included in the lab manual.

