For the SVR12 endpoint analysis, a summary table of the number and proportion of subjects with SVR12, virologic failure, and Other will be created. All subjects who achieve SVR12 will be categorized as SVR12. Virologic failure will be descriptively summarized as “on-treatment virologic failure” and relapse (which will be broken down by study drug completed yes/no). Subjects who do not achieve SVR12 and do not meet criteria for virologic failure will be categorized as Other. The denominator for relapse will be the number of subjects who had HCV RNA < LLOQ on their last observed on-treatment HCV RNA measurement; otherwise, the denominator will be the number of subjects in the FAS. Virologic outcomes will be provided for “SOF/VEL 12 Weeks” and by HCV genotype (1 total [and further broken down for 1a and 1b], 2, 3, 4, 5, and 6 as described above. Separate listings will be provided for subjects with virologic failure and for subjects who meet the criteria for “Other”.

[figure not shown]
In addition, a summary table of the number and proportion of subjects with HCV RNA < LLOQ and \geq LLOQ at the posttreatment follow-up visit (observed and imputed, with reasons for imputation) will be provided for each posttreatment follow-up visit. Results will be displayed for “SOF/VEL 12 Weeks” and by HCV genotype (1 total [and further broken down for 1a and 1b], 2, 3, 4, 5, and 6). The 2-sided 95% Clopper-Pearson exact CIs will be presented for the proportion of subjects with HCV RNA < LLOQ.

Drug resistant substitutions will be analyzed as part of a separate Virology Study Report.

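### Relapse is defined by HCV RNA alone, so a reinfection after suppression would be tabulated as virologic failure, although the planned sequencing samples could tell the two apart

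*SAP*

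**What the plan says.** SAP 6.2.1 lists the proportion with virologic failure as a secondary endpoint, made up of on-treatment failure and relapse. Relapse has three conditions:

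- HCV RNA below LLOQ at end of treatment;
- HCV RNA at or above LLOQ in the post-treatment period;
- that value "confirmed with 2 consecutive values or last available posttreatment measurement".

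SAP 6.2.2 sets out the outcome table. All subjects without SVR12 fall under virologic failure or Other, and Other is residual: "Subjects who do not achieve SVR12 and do not meet criteria for virologic failure will be categorized as Other".

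On sequencing, Protocol 6.6.8 states: "Plasma samples will be collected at Baseline/Day 1 and each subsequent visit for HCV viral sequence analysis". Protocol 6.4 adds a sample at the confirmatory visit. Appendix 2, footnote c, requires one when previously undetectable HCV RNA becomes detectable. SAP 6.2.2 then says: "Drug resistant substitutions will be analyzed as part of a separate Virology Study Report". Nothing in the SAP feeds a sequencing result back into the outcome table. Neither document defines reinfection for this study or gives it an outcome category.

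**The concern.** Relapse means that the treated virus returned. Reinfection means that a new virus was acquired after the treated one was cleared. Only the first is a failure of the drug, but both produce the same HCV RNA pattern. Under the SAP wording, a reinfected subject who was suppressed at end of treatment has to be placed under relapse, because the only alternative category is closed to anyone who meets the failure definition.

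The sponsor has already met such a case. The protocol's ASTRAL-3 summary (1.2.2.1.3) gives two relapse counts for the same SOF/VEL group. Its efficacy results say that "no subjects had on-treatment virologic failure, 11 subjects relapsed, and 2 subjects were lost to follow-up". Its resistance results say: "A total of 10 subjects in the SOF/VEL 12 Week group relapsed, and 1 subject was reinfected".

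Two things are at stake here. Few failures are expected, so one mislabelled subject is a visible share of the failure count. And the study report and the virology report could give different relapse counts for the same subjects, with no stated rule to connect them.

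**Working it through.** **1. Reconcile the ASTRAL-3 counts (Protocol 1.2.2.1.3).** The starting figure is: "In the SOF/VEL 12 Week group, 13 of 277 subjects (4.7%) did not achieve SVR12".

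- Check: 277 − 264 = 13, and 13/277 = 4.7%, as stated.
- Efficacy results: 11 relapsed + 2 lost to follow-up = 13.
- Resistance results: 10 relapsed + 1 reinfected = 11.

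So the reinfected subject is inside the 11 reported as relapse. The failure proportion is 11/277 = 4.0% with that subject and 10/277 = 3.6% without.

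**2. Apply this SAP's wording to a reinfected subject.** Assume HCV RNA below LLOQ at end of treatment, then a different virus at or above LLOQ, either on two consecutive values or at the last available visit. All three conditions in SAP 6.2.1 are met. The subject is a relapse, hence a virologic failure, and cannot be Other.

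**3. Effect on SVR12.** A reinfected subject at or above LLOQ at post-treatment Week 12 is not an SVR12 responder under either label. The primary estimate and its interval do not move.

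**4. Effect on the failure proportion.**

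- Overall: 1/80 = 1.25 points per reclassified subject. For example, 2/80 = 2.5% becomes 1/80 = 1.25%.
- Genotype 3: the target is about 20% of 80, or 16 subjects; 1/16 = 6.25 points. SAP 6.2.2 asks for outcomes by genotype, so this row will appear.
- SAP 6.2.2 uses as the relapse denominator the subjects below LLOQ at their last on-treatment measurement. The shift in the relapse proportion is therefore at least this large.

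**5. How likely is a case?** The documents give no reinfection rate for liver transplant recipients. The only counts are the ASTRAL ones, so the range is an assumption, taking the probability of at least one case in 80 as 1 − (1 − p)^80.

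| Basis for p | p | At least one in 80 |
|---|---|---|
| ASTRAL-1 to -4 (Protocol 1.5) | 1/1302 | about 6% |
| ASTRAL-3 only | 1/277 | about 25% |

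The denominator 1302 agrees with the group sizes: 624 + 134 + 277 + 267. The first row assumes that no reinfection went unreported in the other three trials.

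**6. Share of post-treatment failures.** ASTRAL-3 alone gives 1 in 11 (9%). The other trials add:

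- ASTRAL-1: 2 relapses.
- ASTRAL-2: no SOF/VEL virologic failure.
- ASTRAL-4: 9 genotype 1 and 13 genotype 3 failures, less 2 on-treatment, or about 20.

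The total is 2 + 0 + 11 + 20 = 33, so the pooled share is about 1 in 33 (3%). With k post-treatment failures, the chance that at least one is a reinfection is:

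| k | 1 − (10/11)^k | 1 − (32/33)^k |
|---|---|---|
| 2 | 17% | 6% |
| 4 | 32% | 12% |
| 6 | 44% | 17% |

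**The case against.** The strongest reply is that an RNA-only rule is objective and conservative. It counts every viral return against the drug, and in a single-arm, open-label trial that is safer than a rule that lets failures be removed afterwards. The study is exploratory, no hypothesis is tested, each virologic failure is listed individually (Listing 16.2.6.2), and the virology report can identify a reinfection, as the ASTRAL-3 resistance results did. A change of genotype or subtype is also not proof of reinfection: SAP 3.2 anticipates mixed and indeterminate genotype results, so a minor strain already present at Baseline could grow out and look new.

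Most of this stands, and it determines the form of the fix: the RNA-based count should stay, and a genotype change alone should not suffice. It does not remove the point. Listings show the subject but leave the tabulated label wrong, and a rule written in advance avoids case-by-case judgement once results are known.

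A reader might also infer more than the documents support:

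- *That any detectable post-treatment value counts as relapse.* It does not. Suppression at end of treatment is required, and the value must be confirmed or be the last available.
- *That ASTRAL-3 shows this SAP's rule in operation.* The ASTRAL-3 relapse definition is not in the documents. The example shows the same kind of discrepancy, not provably the same rule.
- *That about 9% of relapses here would be reinfections.* That share comes from the one summarised trial that reports a reinfection, and that trial enrolled only genotype 3.

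**Conclusion.** The point holds as a limited defect of classification. As written, the SAP must label a sequence-proven reinfection after suppression as relapse and virologic failure, although samples that could separate the two are already planned.

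The consequence is confined to descriptive secondary proportions: 1.25 points per subject overall and about 6 points in about 16 genotype 3 subjects. No confidence interval is planned for virologic failure, so no planned inference is affected, and it would be wrong to infer any bias in SVR12.

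Whether a case will occur is uncertain. The 6% to 25% range rests on a single reported reinfection, on the assumption that none went unreported, and on carrying a rate from non-transplant trials into this population. The change is worth making because it is cheap and the sponsor has met the situation before, not because a case is likely.

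**What to change.** In SAP 6.2.1 and 6.2.2:

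1. Keep the RNA-based definition and count of relapse unchanged.
2. Add a line under relapse in the virologic outcome table: of which sequence-confirmed reinfection.
3. Report virologic failure with and without those subjects. They remain non-SVR12 in both.
4. State, before database finalization, that reinfection requires a sequence comparison showing a virus distinct from the Baseline sample, and name the criterion for distinct. A mixed or indeterminate Baseline genotype, an ambiguous comparison or failed sequencing defaults to relapse.
5. Take the classification from the virology analysis, so that both reports carry the same counts.

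The cost is a short SAP addition, one table line and one extra version of a proportion. No new samples are needed. The downside is that the added line waits for sequencing of the few subjects with post-treatment viremia; the RNA-based rows need not wait.

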6.2.2. Analysis Methods for Secondary Efficacy Endpoints

For analyses of HCV RNA $<$ LLOQ by visit while on treatment and during the posttreatment (SVR) follow-up period, subjects will be assigned a value at each visit based on the analysis visit windows specified in Section 3.8.2. Missing values will be imputed based on the categorical imputation rules described in Section 3.6.1. The 2-sided 95% exact CI based on the Clopper-Pearson method will be provided for the proportion of subjects with HCV RNA $<$ LLOQ at each visit for “SOF/VEL 12 Weeks” and by HCV genotype (1 total [and further broken down for 1a and 1b], 2, 3, 4, 5, and 6). The overall category for “HCV RNA $<$ LLOQ” will be split into the following 2 subcategories: “ $<$ LLOQ TND” for subjects with target not detected and “ $<$ LLOQ detected” for subjects with $<$ LLOQ in tabular displays.

Summary statistics will be presented for absolute values and change from baseline in HCV RNA (\log_{10} IU/mL) by visit through the end of treatment. Imputation rules described in Section 3.6.1 will be used to assign HCV RNA values for missing values at a visit that are bracketed by “ $<$ LLOQ TND” and/or “ $<$ LLOQ detected”. Otherwise, a missing = excluded analysis will be performed. Plots of the mean \pm SD and median (Q1, Q3) of absolute values and changes from baseline in HCV RNA through EOT will be presented for “SOF/VEL 12 Weeks” and by HCV genotype (1 total [and further broken down for 1a and 1b], 2, 3, 4, 5, and 6) according to the rules specified above.

For the SVR12 endpoint analysis, a summary table of the number and proportion of subjects with SVR12, virologic failure, and Other will be created. All subjects who achieve SVR12 will be categorized as SVR12. Virologic failure will be descriptively summarized as “on-treatment virologic failure” and relapse (which will be broken down by study drug completed yes/no). Subjects who do not achieve SVR12 and do not meet criteria for virologic failure will be categorized as Other. The denominator for relapse will be the number of subjects who had HCV RNA < LLOQ on their last observed on-treatment HCV RNA measurement; otherwise, the denominator will be the number of subjects in the FAS. Virologic outcomes will be provided for “SOF/VEL 12 Weeks” and by HCV genotype (1 total [and further broken down for 1a and 1b], 2, 3, 4, 5, and 6 as described above. Separate listings will be provided for subjects with virologic failure and for subjects who meet the criteria for “Other”.

[figure not shown]
In addition, a summary table of the number and proportion of subjects with HCV RNA < LLOQ and \geq LLOQ at the posttreatment follow-up visit (observed and imputed, with reasons for imputation) will be provided for each posttreatment follow-up visit. Results will be displayed for “SOF/VEL 12 Weeks” and by HCV genotype (1 total [and further broken down for 1a and 1b], 2, 3, 4, 5, and 6). The 2-sided 95% Clopper-Pearson exact CIs will be presented for the proportion of subjects with HCV RNA < LLOQ.

Drug resistant substitutions will be analyzed as part of a separate Virology Study Report.

6.3. Exploratory Efficacy Endpoints

6.3.1. Definition of Exploratory Efficacy Endpoints

PPD

6.4. Changes From Protocol-Specified Efficacy Analyses

There are no planned changes from protocol-specified efficacy analyses.

7. SAFETY ANALYSES

7.1. Adverse Events and Deaths

7.1.1. Adverse Event Dictionary

Clinical and laboratory adverse events (AEs) will be coded using the current version of MedDRA. System organ class (SOC), high level group term (HLGT), high level term (HLT), preferred term (PT), and lower level term (LLT) will be provided in the AE dataset.

